#### **SYNOPSIS**

Sponsor: Transgene
- IMP1 (Investigational Medicinal Product): Nivolumab, programmed

death receptor-1 (PD-1) blocking antibody (Opdivo\* - BMS)

1MP2: Pexastimogene devactrepose, Vaccinia GMCSF - Thymiding Kinase-Deactivitied Virus (Pexa-Vies - IX504, TO6006 - Transporter) Clinical Protocol: TG6006.01

EudraCT Nº 2016-000085-32 (ND Nº 17439

**Study Title:** A phase I/IIa trial to evaluate the safety and efficacy of the combination of the oncolytic immunotherapy Pexa-Vec with the PD-1 receptor blocking antibody nivolumab in the first-line treatment of advanced hepatocellular carcinoma (HCC)

Coordinating Investigator:

Investigational Centers:

Study Period: Q4 2016 – Q4 2018

Clinical Phase: Phase I/IIa

**Objectives** 

Primary objective

Phase I part: To evaluate the safety profile of intratumoral (IT) Pexa-Vec combined with intravenous (IV) nivolumab in patients with advanced HCC.

[figure not shown]
Phase IIa part: To evaluate the anti-tumor activity and efficacy of IT Pexa-Vec combined with IV nivolumab in patients with advanced HCC with respect to Overall Response Rate (ORR) (RECIST 1.1).

[figure not shown]
Secondary objectives

To evaluate the efficacy of Pexa-Vec combined with nivolumab in patients with advanced HCC with respect to the following endpoints (imaging endpoints evaluated by RECIST 1.1):

- Safety (Phase IIa)
- Disease Control Rate (DCR) at 4 months
- Disease Control Rate (DCR), percent non-progressors over time
- Time to Progression (TTP)
- Duration of Response (DoR)
- Progression Free Survival (PFS), median and proportion of non progressor patients over time
- Overall Survival (OS), median and percent survivors over time
- Blood viral load (HCV, HBV when appropriate)

Exploratory objectives

#### Rationale

HCC is an inflammation-associated cancer that can be considered as an immunogenic tumor for several reasons including the high rate of spontaneous regression for which antitumor immunity has been recognized as a leading mechanism (*Oquinena et al. 2009*), the observations that patients whose tumors contain lymphocytic infiltrates show longer survival and lower risk of recurrence (*Prieto J et al. 2015*, *Wada et al. 1998*) or more recently the encouraging results of clinical trials with check-point blocker antibodies as tremelimumab and nivolumab (*Sangro et al. 2013*, *El-Khoueiry et al. ASCO 2015*).

In addition, there is rising evidence for the PD-1 / PD-L1 pathways involvement in HCC (*Makarova-Rusher et al. 2015*). It was demonstrated that PD-L1 is constitutively expressed in HCC cells in vitro and moreover in tumor specimens in vivo, and elevated PD-L1 expression in HCC is significantly associated with tumor aggressiveness, suggesting that PD-L1 may represent a target for HCC immunotherapy (*Umemoto et al. 2015, Gao et al. 2009*).

These findings have encouraged several clinical studies with PD-1 blockers in HCC. In an ongoing Phase I / II trial (NCT01658878) treatment of mostly 2nd line HCC patients resulted in durable long lasting responses and promising OS at 12 months. The observed response rate in a first set of 42 evaluable patients was 19% which is substantially higher than the 2% observed with sorafenib (*Llovet et al. 2008, Cheng et al. 2009*) and half of the patients (48%) exhibited a disease stabilization (*El-Khoueiry et al. ASCO 2015*). In an ongoing Phase III trial (NCT02576509, Checkmate 459), the efficacy of nivolumab is compared to sorafenib. Another PD-1 blocker, pembrolizumab is currently investigated in 2nd line HCC in Phase II (NCT02702414) and Phase III (NCT02702401) trials. Furthermore, in an ongoing Phase II trial (NCT02519348) in 2nd line HCC, the PD-L1 blocking antibody durvalumab is investigated in combination with the Tremelimumab (anti-CTLA4)

Pexa-Vec is an oncolytic immunotherapy product based on an oncolytic poxvirus expressing granulocyte-macrophage colony-stimulating factor (GM-CSF) which has shown activity in HCC in a dose-finding clinical trial ( $Heo\ et\ al.\ 2013$ ); objective intrahepatic Modified Response Evaluation Criteria in Solid Tumors (mRECIST) (15%) and Choi (62%) response rates and intrahepatic disease control (50%) were equivalent in injected and distant non-injected tumors at both tested doses, i.e.  $1\ x 10^8$  and  $1\ x 10^9$  pfu. Pexa-Vec treatment also improved OS in a dose dependent manner (median

survival of 14.1 months compared to 6.7 months on the high and low dose, respectively; hazard ratio 0.39; P=0.020).

In light of the numerous regulatory mechanisms that HCC tumors employ to evade an immune attack and to overcome the dual liver and tumor immune tolerance phenomena, the use of combination of several immunotherapies offers a great promise and may increase the percentage of patients that respond to immunotherapy.

IMP1 (Investigational Medicinal Product); Nivolomab, programmed death-receptor-1 (PD-1) blocking unibody (Opdivo\* - BMS)

IMP2: Pexastimogene devacinepvec, Vaccinia GMCSF : Thymidine Kinase-Deactivated Virus (Pexa-Vec-2X594, TG6006 - Fransgene)

Clinical Protocot: TG6006.01

EudeaCT Nº 2016-000085-33 IND Nº 17439

The goal of this study is to assess if the combination of these two immunotherapies with different mechanisms of action is feasible, safe and active. Other combinations of oncolytic viruses and immune check-point blockers are under way in other indications.

In this study, a prime injection of Pexa-Vec will be performed before co-administrations of nivolumab and Pexa-Vec; the application of oncolytic virus is expected to induce strong infiltration of innate immune cells to the tumor microenvironment, to trigger molecular changes likely to result in potentiation of Nivolumab (increase in the expression of PD-L1) and to promote the development of an anti-tumoral adaptive immune response.

The present study is conducted in first-line HCC patients with advanced disease but at a moment when their immune responsiveness is still considered adequate. At completion of their participation in the study, all measures will be put in place in order that patients with neither response nor stabilization nor clinical benefit will start Standard of Care without any delay.

#### Methodology

This is a multicenter, open label Phase I/IIa study evaluating the safety and the efficacy of the combination of Pexa-Vec with nivolumab in the first-line treatment of patients with advanced HCC. The Investigational Medicinal Products are Pexa-Vec and nivolumab; patients will be receiving intratumoral (IT) injections of Pexa-Vec in combination with nivolumab intravenous (IV) infusions (Figure 1: IMP administration scheme).

IT Pexa-Vec injections will be performed on D1, D15 and D29. Additional Pexa-Vec boosts may be performed after discussion on a case by case basis between the investigator and Transgene.

Pexa-Vec will be injected into 1 to 5 intrahepatic tumors by a qualified and trained Interventional Radiologist or other trained physician using imaging-guidance (ultrasound and/or CT). As many as possible viable, safely injectable tumors ≥1 cm LD must be treated with a maximum of 5 tumors treated on a given treatment day. Different tumors may be treated on consecutive treatment days. The total prepared injection volume will be divided between 1 to 5 tumors, proportionally to individual tumor volumes. Patients will be monitored closely (e.g., vital signs and clinical observation) the night prior and for 24 hours after the first Pexa-Vec injection as described in the study flow chart (Appendix 1). Hence, hospital admission is required for the first administration of Pexa-Vec. Patients will be monitored the night prior and for at least 8 hours following subsequent Pexa-Vec injections. Longer hospitalization for second, third and additional (boost) administrations of Pexa-Vec is permitted based on Investigator decision.

Nivolumab will be given from D15, by IV route every 2 weeks until progression or unacceptable toxicity. Owing to the possible biphasic evolution of tumor burden often seen with immunotherapeutic products, patients may be treated beyond radiologic progression, under the condition of maintenance of clinical benefit, i.e. stable general status, absence of symptoms and stable hepatic function.

Nivolumab will be administered prior to Pexa-Vec on Days 15 and  $29 \pm 1$  day. Owing to the perception by the investigator of the safety of the administration of the two treatments for a peculiar patient or for logistical reasons, the investigator could distribute the treatment administrations over two consecutive days.

[figure not shown]

Figure 1: IMP administration scheme

#### The study is composed of 2 parts:

#### Phase I part: safety and efficacy will be assessed in 6 patients.

Given the favorable safety profile of both agents, their non-overlapping metabolism, and based on the recently completed study for nivolumab, standard doses will be used for dose level 1 as 3 bi-weekly IT injections of 1x10° pfu for Pexa-Vec and 240 mg IV q2weeks for nivolumab.

The first patient will be monitored for safety after completion of 3 Pexa-Vec IT injections and 2 nivolumab infusions, scheduled on D29 (i.e. week 4), before the second patient can be enrolled. A security interval of 2 weeks between enrolments of each consecutive patients will be applied. In case of a Dose-Limiting Toxicity (DLT) is observed in no more than one patient out of 6 patients and no occurrence of any landmark AE (anticipated effect of the combination), defined as neither increase in severity of hepatic cytolysis, nor significant deterioration of hepatic function (INR, bilirubin, Child-Pugh score), nor increase in number or severity of Pexa-Vec-related skin lesions, nor increase in incidence and severity of immune-related AEs, then accrual in the Phase IIa part of the study will be determined following an analysis by the Independent Safety Committee (ISC) of the safety results in Phase I.

In case of a DLT is observed in more than one patient out of the first 6 patients, or of the occurrence of a landmark AE, one de-escalation regimen is planned:

 Level -1: 3 bi-weekly IT injections of 3x10^8 pfu for Pexa-Vec and 240 mg q2 weeks for nivolumab OR 3 bi-weekly IT injections of 10^9 pfu for Pexa-Vec and 240 mg q3 weeks for nivolumab, depending on the DLT profile relative to the known toxicity of each component of the combination, as judged by the ISC

## Phase IIa part: further evaluation of safety and efficacy, continuation of enrolment up to 30 evaluable patients.

Patients will be further included and treated with Pexa-Vec and nivolumab based on the doses defined in the first part.

Of note, should unexpected toxicities or increased numbers of DLTs in an expanded number of patients occur, de-escalation dose level will also apply.

In both parts, radiological assessments will be performed at Screening and repeated every 6 weeks until documented progression or discontinuation of treatment beyond progression.

Data of locally performed tumor evaluations based on RECIST 1.1 will be used for efficacy assessment. irRC will be assessed centrally for exploratory purposes.

IMPI (Investigational Medicinal Product): Nivolumab, programmed death receptor-1 (PD-1) blocking antibody (Opdivo" - (IMS)

IMP2: Pexastimogene decracirepvec, Vaccinia GMCSF / Thymidine Kinase-Deactivated Virus (Pexa-Vec-, JX594; TG6006 - Transagene)

Clinical Protocol: (G6006.01)

EndraCT N= 2016-000085-33 IND N= 17439

Beyond 12 months of treatment, the evaluations will be performed every 12 weeks until documented progression or discontinuation of treatment beyond progression. If study treatments are stopped before documented radiological progression, PFS visits will be performed every 6 weeks to continue radiological assessment until documented progression.

#### **Number of Patients**

Phase I part: 6 patients (up to 12 patients in case of dose de-escalation)

Phase IIa part: Continue enrolment up to 30 evaluable patients

#### Main Inclusion/Exclusion Criteria

#### **Inclusion Criteria**

- 1. Male or female patients, age ≥18 years old
- 2. Histological/cytological diagnosis of primary HCC, excluding cholangiocarcinoma, hepatocholangiocarcinoma, fibrolamellar carcinoma and hepatoblastoma. Note: if no previous pathological report is available, a tumor diagnostic biopsy should be performed
- 3. Advanced stage HCC per EASL-EORTC (European Association for the Study of the Liver-European Organisation for Research and Treatment of Cancer) guidelines, i.e. patients who are not candidates for curative interventions and not candidates for locoregional modalities
- 4. Patients naïve to systemic therapy for HCC
- 5. Tumor status (as determined by radiology evaluation): At least one measurable viable tumor in the liver, ≥1 cm longest diameter (LD), using a dynamic imaging technique (arterial phase of triphasic computerized tomography [CT] scan, or dynamic contrast-enhanced magnetic resonance imaging [MRI]), and injectable under imaging-guidance (CT or ultrasound)
- 6. At least one tumor that has not received prior local-regional treatment, or that has exhibited definitive growth of viable tumor since prior local-regional treatment of HCC undertaken at least 4 weeks prior to enrolment or 3 months prior to enrolment for radioembolization
- 7. Child-Pugh Class A. Note: paracentesis, albumin infusion or diuretic treatment cannot be used to downgrade Child-Pugh score (e.g., to improve from severe to moderate/mild or from moderate to mild ascites)
- 8. Performance status 0 or 1 on the Eastern Cooperative Oncology Group (ECOG) scale
- 9. Adequate hematological, hepatic, and renal function:
  - a. Hemoglobin ≥9 g/dL
  - b. Platelet count ≥60 10^9/L
  - c. International normalized ratio (INR) ≤1.7
  - d. White blood cell (WBC) count  $\geq 2.10^{9}/L$
  - e. Absolute neutrophil count (ANC)  $\geq 1.10^9$ /L
  - f. Albumin  $\geq$ 28 g/L, total bilirubin  $\leq$ 1.5 times upper limit of normal (ULN); alanine aminotransferase (ALT), aspartate transaminase (AST)  $\leq$ 5 times ULN
  - g. Serum creatinine <20 mg/L or creatinine clearance >60 mL/min according to Cockroft-Gault formula

IMPI (Investigationa) Medicinal Product): Nivolumab, programmed death receptor-1 (PD-1) blocking antibody (Opdivo\* - BMS)

IMP2: Pexastimogene devacirepvec, Vaccinia GMCSF \* Thymidine Kinase-Deactivated Virus (Pexa-Vec., JX594, TG6006 - Transgene)

Clinical Protocol: TG6006.61

EndroCT Nº 2016-000085-32 IND Nº 17439

- 10. For patients who are sexually active: willing to use adequate barrier contraception method during Pexa-Vec and nivolumab treatment period, for at least 6 weeks after last Pexa-Vec injection and for at least 5 months after last nivolumab administration
- 11. Life expectancy of at least 3 months
- 12. Patient should agree to undergo a pre-treatment tumor biopsy, if necessary for diagnostic purposes; a post-treatment tumor biopsy is optional for translational research purposes
- 13. Written informed consent
- 14. Patients with active hepatitis B infection should be on adequate antiviral therapy
- 15. Cardiology consultation and clearance obtained for study participation. Baseline cardiologic investigations should include troponin T or I blood level measurement, electrocardiogram (ECG) and cardiac echography (ECHO) with measurement of left ventricular ejection fraction (LVEF). Ability to temporarily suspend treatment with anti-hypertensive medications should also be assessed.

#### **Exclusion Criteria**

- 1. Major surgery within 4 weeks of study treatments (minor surgical procedures are allowed e.g., intravascular access line or Port-a-Cath®)
- 2. Local-regional therapy of HCC within 4 weeks or radioembolization within 3 months prior to enrolment
- 3. Histological diagnosis of cholangiocarcinoma, hepatocholangiocarcinoma, fibrolamellar carcinoma and hepatoblastoma
- 4. History of moderate or severe ascites, bleeding esophageal varices, hepatic encephalopathy or pleural effusions related to liver insufficiency within 6 months of screening; patients with adequately treated esophageal varices (banding, sclerotherapy) are allowed
- Clinically significant ascites, e.g., requiring a paracentesis or aggressive inpatient diuresis, pericardial and/or pleural effusions. Minimal, medically controlled ascites detectable on imaging studies only and not precluding a safe IT injection of Pexa-Vec- is allowed.
- 6. Active, known or suspected significant immunodeficiency due to underlying illness including HIV/AIDS, autoimmune diseases, and/or immune-suppressive medication including high-dose corticosteroids (defined as ≥20 mg/day prednisone or equivalent which is ongoing at the time of randomization and/or was taken for more than 4 weeks within the preceding 2 months of study treatment)
- 7. Any prior or planned organ transplant (e.g., liver transplant)
- 8. History of severe eczema and/or ongoing severe inflammatory skin condition (as determined by the Investigator) requiring medical treatment
- 9. Patients who experienced a severe systemic reaction or side-effect as a result of a previous vaccination with vaccinia
- 10. Pregnant or nursing (lactating) women, where pregnancy is defined as the state of a female after conception and until the termination of gestation. Child-bearing potential patients with a positive hCG laboratory test (>10 mIU/mL) at screening and/or a urinary pregnancy test at Baseline will perform an ultrasound to confirm the pregnancy.

IMP1 (Investigational Medicinal Product): Nivolumab, programmed death receptor-1 (PD-1) blocking antibody (Opdivo" - HAIS)
IMP2: Pexastimogene devacirence, Vaccinia GMCSF / Invinitine

Clinical Protocol: 10:6006.01

[ND Nº 17430

Kinase-Deactivited Virus (Pexa-Vec., TX594, TG6006 - Transgene)

- 11. Prior malignancy except for the following: adequately treated basal or squamous cell skin cancer, in situ cervical cancer, adequately treated cancer from which the patient has been disease-free for at least 3 years
- 12. Tumor(s) invading a major vascular structure (e.g., carotid artery) or other key anatomical structure (e.g., pulmonary airway) in the event of post-injection tumor swelling and/or necrosis (hepatic and portal vein involvement allowed)
- 13. Viable central nervous system malignancy
- 14. Symptomatic cardiovascular disease, including but not limited to significant coronary artery disease (e.g., requiring angioplasty or stenting) or congestive heart failure within the preceding 12 months
- 15. Current or past history of cardiovascular disease (e.g., past history of myocardial infarction, ischemic cardiomyopathy) unless cardiology consultation and clearance has been obtained for study participation
- 16. Medical conditions, per the investigator's judgment, that would contra-indicate volume loading (e.g., intravenous |[IV] fluid bolus infusion) or increase the risk of severe hypotension following treatment with Pexa-Vec (e.g., dehydration, hypovolemia).
- 17. Other medical condition or laboratory abnormality or active infection that in the judgment of the Principal Investigator may increase the risk associated with study participation or may interfere with interpretation of study results and/or otherwise make the patient inappropriate for entry into this study
- 18. Significant bleeding event due to abnormal blood clotting within the last 3 months that places the patient at risk for intrahepatic IT injection procedure based on Investigator assessment
- 19. Anticoagulant or anti-platelet medication that cannot be interrupted prior to Pexa-Vec- IT injections, including:
  - Aspirin that cannot be discontinued for 7 days prior to Pexa-Vec- IT injections
  - Coumadin that cannot be discontinued for 7 days prior to Pexa-Vec- IT injections
  - Low molecular weight heparin (LMWH) that cannot be discontinued >24 hours prior to Pexa-Vec- IT injections
  - Unfractionated heparin (UFH) that cannot be discontinued >4 hours prior to Pexa-Vec- IT injection
  - Oral direct thrombin inhibitor (dabigatran) or direct Factor Xa inhibitor (rivaroxaban, apixiban, and endoxaban) that cannot be discontinued for 4 days prior to Pexa-Vec- IT injection
- **NOTE:** LMWH or UFH may be used to transition patients on and off of the above anti-coagulants (if deemed appropriate by the treating physician) prior to Pexa-Vec- treatments as long as the last dose of LMWH is administered >24 hours prior to treatments and last dose of UFH is administered >4 hours prior to treatments.
- 20. Hepatitis C virus therapy including interferon/pegylated interferon or ribavirin that cannot be discontinued within 14 days prior to any Pexa-Vec injection. Medical Monitor should be consulted if the patient is taking any other antiviral medications to determine eligibility, on the grounds of interference with Pexa-Vec replication properties.
- 21. Inability to suspend treatment with anti-hypertensive medication (including but not limited to: diuretics, beta-blockers, angiotensin converting enzyme [ACE] inhibitors, aldosterone

IMP1 (Investigational Medicinal Product): Nivolemah, programmed death receptor-1 (PD-1) blocking antibody (Opdivo\* - BMS)

1MP2) Pesastimogene devacirepvee. Vaccinia GMCSF - Thymidine

Clinical Protocol: 1(16005.01

EudraC UN° 2016-000085-32 IND N° 17439

antagonists, etc.) for 48 hours prior to and 48 hours after each Pexa-Vec injection, as assessed at the screening cardiology consultation.

- 22. Any known allergy or reaction to any component of nivolumab formulation or its excipients
- 23. Prior exposure to cancer immunotherapy including any immune checkpoint inhibitor, cancer vaccine and/or oncolytic virus
- 24. Participation in a clinical study and treatment with an active IMP within 4 weeks prior to randomization
- 25. Pulse oximetry O2 saturation <90% at rest on room air
- 26. Patient unable or unwilling to comply with the protocol requirements.

#### Investigational Medicinal Products (IMPs), Dose, Mode of Administration

#### Pexa-Vec

Pexa-Vec (pexastimogene devacirepvec; investigational product code: JX-594, TG6006) is a replication-competent, transgene-expressing therapeutic vaccinia virus derived from the Wyeth vaccine strain (Dryvax-®, Wyeth Laboratories). Three genetic modifications are included:

- 1. thymidine kinase (TK) gene deactivation,
- 2. granulocyte macrophage colony stimulating factor (GM-CSF) gene insertion under control of the synthetic early-late promoter, and
- 3. lac-Z gene insertion under control of the p7.5 promoter.

Pexa-Vec- viral suspension will be supplied in individual 4-mL glass vials with a recoverable volume of 2 mL per vial and an infectious titer of  $1 \times 10^9$  pfu (9.0 Log 10 plaque-forming units (pfu)). Each vial is intended for single use (i.e., one injection to one patient).

Patients will receive three IT injections of Pexa-Vec at the dose of  $1 \times 10^9$  pfu per treatment, every 2 weeks.

Additional Pexa-Vec boosts may be performed from Week 12 in patients based on a case by case discussion between the investigator and Transgene.

#### Nivolumab

Nivolumab is a programmed death receptor-1 (PD-1) blocking antibody. It will be supplied in 40 and/or 100 mg vials (10 mg/mL).

Patients will be administered as an IV infusion over 60 minutes every 2 weeks, with the targeted dose of 240 mg.

Accounting for the immunotherapeutic effect of both drugs and for the peculiar kinetics of clinical efficacy of these treatments, guidance is provided to continue treatment beyond evidence of radiologic progression.

#### **Associated Therapies**

The use of antiemetics, antipyretics, antidepressants, biphosphonates, vitamin B12 and vitamin D will not be restricted during the course of the study.

Thrombopoietin, erythropoietin and G-CSF will not be allowed throughout DLT period.

IMP1 (Investigational Medicinal Product); Nivolumab, programmed death receptor-1 (PD-1) blocking untibody (Opdivo\* - BMS)

IMP2: Pexastimogene devacirepyoe. Vaccinia GMCSF / Thymidine Kinnse-Deantivarel Virus (Pexas Voc., 18804-16600). Transagno.

Clinical Protocol: 166006.01

EndraCT Nº 2016-000083-32/ IND Nº 17439

Oral or parenteral corticosteroids may attenuate potential beneficial immunologic effects of treatment with nivolumab and Pexa-Vec and should not be used but may be administered at the discretion of the treating physician if needed. Alternatives to corticosteroids should be considered if feasible. The use of inhaled corticosteroids and mineralocorticoids (e.g. fludrocortisone) is allowed.

Antihypertensives (including diuretics) must be discontinued at least 48 hours prior to each Pexa-Vec- injection and restarted no earlier than 48 hours after the injection.

Unless contraindicated, all patients will be pre-medicated with acetaminophen (paracetamol) ibuprofen and esomeprazole on each Pexa-Vec treatment day according to the following scheme:

- acetaminophen 1000 mg at 2 hours pre-injection, 6 hours, 14 hours and 22 hours post-injection,
- ibuprofen 400 mg at 2 hours, 10 hours and 18 hours post-injection,
- esomeprazole 40 mg, or equivalent.

In case of contra-indication to the prescription of ibuprofen, due to underlying advanced cirrhosis, the investigator may alternatively use the following regimen based on acetaminophen (paracetamol) or equivalent antipyretics, (unless contraindicated):

- 500–1000 mg at 2 hours pre-infusion/injection,
- 500–1000 mg at 4 hours post-procedure,
- 500–1000 mg every 6 hours thereafter, as needed (the total acetaminophen dose should be carefully assessed to avoid cumulative toxicity).

Any treatment may be continued if deemed necessary.

Fevers may be associated with onset of rigors. Meperidine or equivalent may be used for severe rigors.

Unless contra-indicated, patients should also be pre-hydrated with approximately 1 L of solute-containing fluids IV or orally within 12 hours of treatment initiation. In addition, during the post-treatment observation period, patients should receive IV solute-containing fluids or other appropriate treatment as needed for blood pressure support.

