# 11.1 Blood pharmacokinetics of Pexa-Vec

# 11.2 Blood pharmacokinetics of nivolumab

# 11.3 Other laboratory analyses

### 12 STATISTICAL METHODS PLANNED AND SAMPLE SIZE

## 12.1 Determination of sample size

## **Hypothesis**

As the patient survival benefit may be correlated with either radiological response of tumors or/and prolonged stabilization of the disease, the analysis of efficacy will consider ORR as primary endpoint. Sample size justification will use available data on ORR, as such: in a Phase I/II trial, 8/42 (19%) patients with previously treated HCC experienced an objective response when treated with single-agent nivolumab (El-Khoueiry et al., ASCO 2015). Therefore, a response rate of 15%-20% with the combination of Pexa-Vec + nivolumab in these patients would be considered disappointing, while a response rate of 35% or more would be promising and would encourage further study of the regimen in these patients. The null hypothesis for response rate H0 is set at 15%, the alternate hypothesis of efficacy is set at HA=35%, the type I error α is set at 5% one sided and the power is set at 80%.

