#### 12.5 Protocol deviations

Any protocol deviation will be discussed with the Investigator on a case by case basis, and characterized as minor or major. Patients with deviations deemed major cannot be included in per protocol analyzes and should be replaced. Anticipated but not limited major deviations are:

- Failure to complete all 3 IT Pexa-Vec injections and 2 nivolumab IV infusions in the Phase I part, 2 IT Pexa-Vec injections and 2 nivolumab IV infusions in the Phase IIa part,
- No histological confirmation of HCC.
- Previous systemic therapy for HCC,
- Child-Pugh score beyond A, or deteriorated hepatic function beyond score, or advanced cirrhosis diagnosis based on albuminemia, INR, bilirubin blood levels and clinical symptoms: uncontrolled ascites or esophageal varices, etc.
- ECOG PS > 1,
- Prohibited concomitant medications or no withdrawal of anti-hypertensive, anticoagulant or anti-platelet medications within protocol-specified conditions,
- Immunologic deficiency,
- Pregnancy and breast-feeding.

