# Anticipated but not limited major deviations are:

- Failure to complete all 3 IT Pexa-Vec injections and 2 nivolumab IV infusions in the absence of DLT in the Phase I part, 2 IT Pexa-Vec injections and 2 nivolumab IV infusions in the Phase IIa part,
- No histological confirmation of HCC,
- Previous systemic therapy for HCC,
- Child-Pugh score beyond A, or deteriorated hepatic function beyond score, or advanced cirrhosis diagnosis based on albuminemia, INR, bilirubin blood levels and clinical symptoms: uncontrolled ascites or esophageal varices, etc.
- ECOG PS > 1,
- Prohibited concomitant medications or no withdrawal of anti-hypertensive, anticoagulant or anti-platelet medications within protocol-specified conditions,
- Immunodeficiency,
- Pregnancy and breast-feeding.

GCP deviations (including protocol deviations, applicable SOPs deviations etc) must be tracked. Transgene shall be provided with a deviation listing before the data review meeting. The criticality of each deviation will be established in agreement with Transgene during the data review meeting (at the latest) in order to define the different populations for analyses.

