## 8.5 Protocol deviation summaries

All protocol deviations for enrolled patients will be presented by patient in data listings with a distinction between deviations at inclusion and deviations during the study.

The number of patients with at least one major protocol deviation will be summarized by type and overall with a distinction between deviations at inclusion and deviations during the study. All protocol deviations will be reviewed before database lock during the Data Review Meeting.

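### The hepatic and ECOG major-deviation items have no cut-off or time point and reach wider than the entry criteria, so treated patients can be removed from the primary ORR set and replaced

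*Protocol*

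**What the plan says.** Protocol 12.5 and SAP 6.2 carry the same item in their lists of anticipated major deviations: "Child-Pugh score beyond A, or deteriorated hepatic function beyond score, or advanced cirrhosis diagnosis based on albuminemia, INR, bilirubin blood levels and clinical symptoms". The clinical symptoms named are uncontrolled ascites or esophageal varices, and the list is left open. ECOG PS above 1 is a separate item. Protocol 12.5 gives the consequence: "Patients with deviations deemed major cannot be included in per protocol analyzes and should be replaced". The per protocol (PP) population is the primary efficacy set (protocol 12.3.3 and 12.6; SAP 6 and 6.1).

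Entry is defined by numbered limits (protocol 4.1 and 4.2):
- Child-Pugh class A (inclusion 7) and ECOG 0 or 1 (inclusion 8);
- an INR limit (9c), albumin of at least 28 g/L and bilirubin of at most 1.5 times ULN (9f);
- no recent moderate or severe ascites, bleeding varices or encephalopathy (exclusion 4), and no clinically significant ascites (exclusion 5);
- investigator judgement on other conditions (exclusion 17).

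Exclusion 4 adds that "patients with adequately treated esophageal varices (banding, sclerotherapy) are allowed". The synopsis (Associated Therapies) and protocol 6.1.2.1 provide for treated patients with advanced cirrhosis: "In case of contra-indication to the prescription of ibuprofen, due to underlying advanced cirrhosis, the investigator may alternatively use the following regimen".

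Deviations are classed as minor or major case by case (protocol 12.5). The class is settled with the sponsor by the data review meeting at the latest (SAP 6.2 and 7.5). SAP 8.5 summarizes major deviations "with a distinction between deviations at inclusion and deviations during the study".

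**The concern.** The three parts of the hepatic item are joined by *or*. The second and third parts add something only for a patient who is still Child-Pugh A, and neither has a threshold. SAP 8.3.1 records cirrhosis as yes or no, plus the Child-Pugh components, so no variable defines advanced cirrhosis. A patient can be inside every numeric entry limit, be treated under the protocol's own premedication clause, and still be classed as a major deviation.

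Nor does either item say when it applies. Protocol 8.2 lists Child-Pugh scoring at screening, but ECOG is recorded at each visit, and bilirubin, albumin and INR are repeated on study. Other items on the list, such as incomplete dosing and prohibited medication, are on-study events. Decline after treatment, which is an outcome, can therefore be read as a deviation.

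At stake is the primary result. If the patients removed respond less often than the rest, replacing them raises the PP response rate. The trial is open-label and local responses may be known when the classification is made.

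**Working it through.** **Inputs from the plan** (protocol 12.1; SAP 7.1 and 7.3.3). "The null hypothesis for response rate H0 is set at 15"%; "the alternate hypothesis of efficacy is set at HA=35"%; the type I error "is set at 5% one sided and the power is set at 80"%. At 15 evaluable patients, 3 or fewer responses allow a futility stop (non-binding) and 6 or more reject H0. At 30, 8 or more reject H0.

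**Reproducing the design.** With Lan-DeMets O'Brien-Fleming spending at half information, the critical values are 2.538 and 1.662. Using the variance under H0:
- interim: 0.15 + 2.538 × √(0.15 × 0.85 / 15) = 0.384, which is 5.76 of 15, so 6;
- final: 0.15 + 1.662 × √(0.15 × 0.85 / 30) = 0.258, which is 7.75 of 30, so 8.

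The Pocock-type futility bound is 20.8%, or 3.1 of 15, so 3. Power at N = 30 is 80.3%, with the variance under HA used for power. The stated cut-offs and the stated 80% all reproduce.

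**Inputs not in the plan (assumptions).** The true ORR in all treated patients is 15%. A share f is removed under these items and responds at rate r. I take f = 10% and 20%, and r = 0 and 5%. For scale, the plan's whole allowance for non-evaluable patients is 10% (protocol 3.1.2: 42 / 0.9 = 46.7, so 47). The 20% case is therefore an upper scenario.

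**Formulas.** Retained (PP) rate: p = (0.15 − f × r) / (1 − f). Let X and Y be the responses in the first and second 15 PP patients.
- A = P(X ≥ 6)
- B = sum over x = 4, 5 of P(X = x) × P(Y ≥ 8 − x)
- C = the same sum over x = 0 to 3

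The chance of declaring success is A + B with futility followed and A + B + C with futility ignored.

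| f | r | p | A | B | C | Futility followed | Futility ignored |
|---|---|---|---|---|---|---|---|
| 0 | – | 0.1500 | 0.0168 | 0.0383 | 0.0192 | 5.5% | 7.4% |
| 10% | 5% | 0.145 / 0.9 = 0.1611 | 0.0235 | 0.0533 | 0.0261 | 7.7% | 10.3% |
| 10% | 0 | 0.150 / 0.9 = 0.1667 | 0.0274 | 0.0620 | 0.0300 | 8.9% | 11.9% |
| 20% | 5% | 0.140 / 0.8 = 0.1750 | 0.0341 | 0.0764 | 0.0364 | 11.1% | 14.7% |
| 20% | 0 | 0.150 / 0.8 = 0.1875 | 0.0463 | 0.1008 | 0.0467 | 14.7% | 19.4% |

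The first row exceeds 5% because the plan uses a normal approximation. That is a separate matter; only the rise from the first row belongs to this point.

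**A single-trial illustration.** A result of 8/30 (26.7%) in PP, with 3 non-responders removed and replaced, is 8/33 = 24.2% once they are counted.

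**The case against.** Much of the hepatic item restates eligibility. Inclusions 7, 9c and 9f and exclusions 4, 5 and 17 cover most of the markers it names. A reader might infer that no entry criterion excludes these patients; the documents do not support that. The defect is wording that is undefined and wider than the limits.

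A reader might also see a direct clash between varices as a sign of advanced cirrhosis and the allowance for treated varices. The adjective *uncontrolled* plausibly governs varices as well as ascites, and then there is no clash. The premedication clause is permissive and concerns advanced cirrhosis only. It says nothing about liver function worse than the score.

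Removal is not automatic, because classification is case by case. Most neighbouring items, such as no histology or prior systemic therapy, are entry matters, so ECOG above 1 is naturally read at entry. SAP 8.5 separates deviations at inclusion from those during the study but never says that clinical decline is one.

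Finally, efficacy is repeated in the ITT population of all treated patients (SAP 6 and 8.7), so a gap between PP and ITT would show.

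All of this narrows the point. It does not supply a cut-off, a time point or agreement with the premedication clause. The ITT repeat shows a gap but does not carry the decision, because the 8-of-30 rule is stated for evaluable patients and PP is the primary set (SAP 8.7 and 8.7.1).

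**Conclusion.** The point holds in this limited form. The hepatic and ECOG deviation items are open-ended, wider than the entry criteria, and at odds with the clause that foresees treating patients with advanced cirrhosis. They act on the primary set through removal and replacement, and may be applied after responses are known.

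Under the assumptions above, removing 10% raises the chance of declaring success at a true 15% ORR by 2.2 to 3.4 percentage points with futility followed (7.7 − 5.5 and 8.9 − 5.5). With futility ignored the rise is 2.9 to 4.5 points (10.3 − 7.4 and 11.9 − 7.4). At 20% removed the chance is 11.1–14.7% with futility followed and 14.7–19.4% with it ignored.

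A reader might infer from the larger figures that the false-positive rate will double or more. The documents do not support that as a prediction. They give neither the share affected nor its response rate, lower response in these patients is itself an inference, and 20% for this one cause is twice the plan's total allowance for non-evaluable patients. What is established is a route to upward bias in a 30-patient trial decided at 8 responses, worth closing before the classification is made.

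**What to change.** In protocol 12.5 and SAP 6.2:
- Limit the hepatic and ECOG items to a breach, at baseline, of the numbered entry criteria: inclusions 7, 8, 9c and 9f, and exclusions 4 and 5.
- Delete the wording on function beyond the score and on an advanced-cirrhosis diagnosis as grounds for leaving the PP set.
- State that on-study decline in Child-Pugh or ECOG is not a deviation.

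Two sets of passages must also be reconciled: the premedication clause (synopsis, Associated Therapies, and protocol 6.1.2.1) with the deviation list, and the INR limit in 9c, which is at most 1.7 in the synopsis and below 1.7 in protocol 4.1. This review does not say which clinical rule is right.

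The cost is about two lines in each document. N = 30, the interim at 15 and all cut-offs stay as they are. A few more patients remain in the primary set, and the observed ORR may be slightly lower.
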